2.3 Design Justification

DLD, which includes night vision disturbances, affects patients under mesopic or scotopic conditions. DLD involves photic phenomena, such as glare, halos, and starbursts, which can be a result of a combination of ocular aberrations and light scatter, as well as the effect of multiple images simultaneously superimposed onto the retina, as in the case of multifocal intraocular lenses (IOLs; [Rosen 2005](#)).

These visual disturbances can be debilitating to a variety of everyday activities, especially driving. The light emitted by traffic lights and other cars scatters and obscures most of the visual field, making driving in dim light conditions hazardous. Glare, in particular, can be dangerous while driving.

Several surveys suggest that DLD are a clinically relevant concern.

- More than half (53%) of vision-corrected Americans admit they feel uncomfortable when driving in the dark ([Fejer and Girgis, 1992](#)).
- Up to 3% of patients with refractive procedures are unable to function visually at night ([Pop and Payette, 2004](#); [Fan-Paul, 2002](#); [Holladay, 1999](#); [Monestam and Lundqvist, 2006](#)).
- As many as 20% of people with multifocal IOLs complain of night vision disturbances ([van Alphen, 1976](#)).
- In one study of 297 drivers given vision tests that correlate with accidents, 45% of the drivers who reported difficulty driving at night were unable to perform any of the tests with glare ([Puell, 2004](#)).

The effects of DLD can be mitigated by miosis, where the smaller pupil blocks the unfocused, peripheral aberrant rays of light, selectively allowing passage of the more centrally focused rays (Martinez, 1998). A miotic change in the pupil size can be achieved by modulating 1 of 2 or both opposing sets of muscles – the iris sphincter muscles controlled by the cholinergic nervous system and the iris dilator muscles controlled by the adrenergic nervous system (Yoshitomi, 1985; Steinhauer, 2004). An alpha-1 antagonist approach will act on the iris dilator muscle and produce a miotic effect (Yu, 2002). It is proposed that a moderate pharmacologic reduction of pupil size (20–25%) by the application of an alpha-1 antagonist has the potential to mitigate DLD in many affected individuals.

The biggest challenge for the treatment of DLD is the lack of safe, tolerable, convenient, and effective treatments. Despite a large number of addressable patients with moderate-to-severe DLD, there is no FDA-approved treatment on the market for DLD. Some commonly used tools such as tinted glasses are not effective, and in fact, may worsen patients' vision at night. Off-label use of approved miotic agents, such as regular-strength pilocarpine, are unsuitable for the treatment of DLD because they reduce pupil size to a degree that may impede safe night vision and may cause loss of accommodation (Isopto prescribing information).

Phentolamine is a non-selective alpha-1 and alpha-2 adrenergic antagonist acting on adrenergic receptors and is known to inhibit contraction of the iris dilator muscle, resulting in a smaller pupil size.

Previous Phase 2 clinical trials showed that 1.0% Phentolamine Mesylate Ophthalmic Solution (0.75% Phentolamine Ophthalmic Solution) significantly decreases PD and improves mLCVA in DLD subjects after single- and multi-dose (14 days) treatment. Phentolamine Ophthalmic Solution was generally well-tolerated in the eye (the most common complaint was mild-to-moderate ocular hyperemia and eye irritation) and there were no clinically meaningful systemic effects as measured by HR and BP.

2.4 Route of Administration, Dosage Regimen, and Treatment Period

As the intended route of administration for Nyxol is topical ocular, this is the route to be used in this study.

The dose for one drop of Nyxol selected for this study, 0.75%, was based upon: 1) preclinical safety studies, 2) the results of the previous ophthalmic clinical studies described above and in the IB, and 3) clinical studies conducted with varying doses of drugs in the same class (Hogan, 1997).

Treatment (Nyxol or placebo) will be administered OU. Subjects will have one drop of treatment administered in each eye.

Note that 0.75% Phentolamine Ophthalmic Solution, which expresses the phentolamine mesylate concentration in free base, is the new nomenclature being used in place of 1% Phentolamine Mesylate Ophthalmic Solution, which was how Nyxol had been described in prior studies.

2.5 Compliance

This study will be conducted in compliance with the protocol and in accordance with Good Clinical Practice (GCP), the ethical principles set forth in the Declaration of Helsinki and with the US Code of Federal Regulations.

2.6 Study Population

A sample size of approximately 160 DLD subjects \geq 18 years of age will be randomized in a 1:1 ratio to 1 of 2 masked treatment arms (Nyxol or placebo), with the expectation that approximately 136 subjects will be evaluable for efficacy. Randomization will be stratified by iris color (light/dark irides; [Appendix 1](#)). The subjects will be recruited from approximately 15 investigational sites.

3 OBJECTIVES AND PURPOSE

The LYNX-1 study is a randomized, placebo-controlled, double-masked, multiple-dose study of the safety and efficacy of Nyxol (0.75% Phentolamine Ophthalmic Solution) in subjects with DLD.

The objectives of this study are:

- To evaluate the efficacy of Nyxol to improve mLcVA in subjects with DLD
- To evaluate the efficacy of Nyxol to improve visual performance
- To evaluate the safety of Nyxol
- To evaluate any additional benefits of Nyxol in treating DLD subjects

The Sponsor intends to use this first Phase 3 registration study to evaluate Nyxol for the indication of [REDACTED]
[REDACTED]

4 STUDY DESIGN

4.1 Primary and Secondary Endpoints

Efficacy:

The primary efficacy endpoint is the percent of subjects with ≥ 15 ETDRS letters (≥ 3 lines) of improvement in the study eye compared to baseline in monocular mLCVA at Day 8.

The eye with the greatest mLCVA improvement [REDACTED]

[REDACTED]
[REDACTED]
[REDACTED]
[REDACTED]
[REDACTED]

[REDACTED] The study eye and non-study eye, as well as binocular, will both be evaluated at all appropriate assessments.

All treatments will be administered OU.

Secondary efficacy endpoints (for the study eye, the non-study eye, the best of either eye, and binocular) will include:

- [REDACTED]
[REDACTED]
[REDACTED]
- [REDACTED]
[REDACTED]
- [REDACTED]
[REDACTED]
[REDACTED]
[REDACTED]
- [REDACTED]
[REDACTED]
- [REDACTED]
[REDACTED]
[REDACTED]
- [REDACTED]
[REDACTED]

Exploratory efficacy endpoints (for the study eye, the non-study eye, the best of either eye, and binocular) will be collected and analyzed for the sites that have an OPD Scanner and will include but are not limited to:

- [REDACTED]
- [REDACTED]
- [REDACTED]

In addition, data captured by OPD Scan III per subject per applicable visit will be generated. These data include graphs, heatmaps, vision simulations, numerical data, point spread function, Zernike graphs, VA-ETDRS simulations, angle kappa, etc. Exploratory analyses may be completed using these data.

Measurements (Appendix 2):

Safety:

The primary safety measures are conjunctival hyperemia and AEs.

Analysis for conjunctival hyperemia includes change from baseline (Day 1) in the conjunctival hyperemia grading scale (CCLRU images) at each visit (Day 8 and Day 15), for study eye and non-study eye. Any increase of 2 units in conjunctival hyperemia between consecutive visits is considered an AE.

Other safety measures include IOP, biomicroscopy, ophthalmoscopy, dry eye measurements, and systemic safety as measured by HR and BP. Urine pregnancy tests for females of childbearing potential will be conducted.

Subject questionnaire values will be summarized by treatment group and visits (Day 1, Day 8, and Day 15).

Measurements:

- Conjunctival hyperemia will be assessed visually with a grading scale (0-3) using images from the CCLRU.
- IOP will be measured with the Tono-Pen.
- BP and HR will be measured manually or with available digital devices.
- Subject questionnaire will be a brief symptom survey ([Appendix 3](#)).

4.2 Description and Schedule of Visits and Procedures

A sample size of approximately 160 DLD subjects ≥ 18 years of age will be randomized in a 1:1 ratio to 1 of 2 treatment arms (Nyxol or placebo), with the expectation that approximately 136 subjects will be evaluable for efficacy. Randomization will be stratified by iris color (light/dark irides). Study procedures are shown in detail in [Table 2](#).

Table 2 Screening, Baseline, Treatment, and Follow-Up Visits and Procedures

	Screening/Baseline [a]	Treatment	Treatment	TC Follow- Up
[REDACTED]	■	■	■	
[REDACTED]	■	■	■	
[REDACTED]	■	■	■	
[REDACTED]	■	■	■	
[REDACTED]	■	■	■	
[REDACTED]	■	■	■	
[REDACTED]	■	■	■	
[REDACTED]	■		■	
[REDACTED]	■		■	
Adverse events	X	X	X	X
Randomization number assigned	X			
Medications dispensed/Re- dispensed	X	X		
Diary dispensed/Re-dispensed	X	X		

Abbreviations: BAT, Brightness Acuity Tester; BCDVA, best-corrected distance visual acuity; CCLRU, Cornea and Contact Lens Research Unit; DCNVA, distance-corrected near visual acuity; mLcVA, mesopic low-contrast visual acuity

4.3 Measures Taken to Minimize/Avoid Bias

This is a placebo-controlled, double-masked, 1:1 randomized, 2-arm, Phase 3 study.

4.4 Study Medications

Study Medication Identification

Established name	Phentolamine mesylate – parent phentolamine
CAS registry number	65-28-1 – parent 50-60-2
Chemical class	An alpha-adrenergic antagonist, it is a member of the following classes: imidazoles, of phenols, is a tertiary amino compound and a substituted aniline
Chemical name	3-[N-(4,5-dihydro-1H-imidazol-2-ylmethyl)-4-methylanilino]phenol; methanesulfonic acid
Molecular formula	$C_{18}H_{23}N_3O_4S$ – parent $C_{17}H_{19}N_3O$
Molecular weight	377.140 – parent 281.352
Drug name/formulation	Nyxol / aqueous isotonic solution
Concentration active	1% – parent 0.75%
Manufacturer drug substance	[REDACTED]
Manufacturer drug product, placebo	[REDACTED]
Storage requirements	[REDACTED] [REDACTED] [REDACTED] [REDACTED] Stored in a secured location (locked) with no access for unauthorized personnel at site

Formulation

Nyxol (0.75% Phentolamine Ophthalmic Solution) is a clear, colorless to slightly brown, sterile, non-preserved, isotonic, buffered aqueous solution containing 1% phentolamine mesylate (equivalent to 0.75% phentolamine free base), [REDACTED]. Placebo for Nyxol is a clear, colorless, sterile, non-preserved, isotonic, buffered aqueous solution containing [REDACTED]. The pH of the study medications may be adjusted with [REDACTED] (United States Pharmacopeia [USP]) and/or [REDACTED] (USP) to [REDACTED].

4.4.1 *Packaging and Labeling*

The investigational products, active and placebo, are packaged in a unit-of-use 1 mL low-density polyethylene (LDPE) dropper bottles with a fill volume specification of 0.6 mL for single-dose investigational use. Each bottle is wrapped with an aluminum foil overwrap impermeable to water and oxygen and will be labeled with an investigational label showing the study protocol number and other relevant information, including a statement “Caution – New Drug – Limited by Federal (US) Law to Investigational Use”.

4.4.2 *Storage of Study Medication and Dispensing*

Prior to dispensing, all investigational material must be stored in a secure location with strictly limited access documented by signature of authorized persons who may dispense investigational materials.

[REDACTED]
[REDACTED]
[REDACTED] medication must not be frozen and must

be protected from light. All investigational study medication must be stored in a secure facility, with access limited to the Investigator and authorized staff.

4.4.3 *Study Medication Administration*

Study medication will be dispensed by the Investigator or designee at the site on Visit 1 (Screening/Baseline).

The subject will instill one drop once daily (QD) at or near bedtime (8PM to 10PM) OU for 14 days (+ 1 day). The first dose of study medication will be taken at 8PM to 10PM on the evening of the Baseline Visit (Day 1). If the subject wears contact lenses, they must be removed prior to dosing and not replaced until the next morning at the earliest.

4.4.4 *Study Medication Accountability*

4.4.4.1 Receipt and Disposition of Study Medication

The Investigator or designee (e.g., study coordinator or pharmacist) shall maintain a full accountability record for the study medication and will be responsible for recording the receipt, dispensing, and return of all supplies of the study drug using the inventories supplied by the Sponsor. Each subject will receive sufficient study medication for the duration of the trial. A study medication box will be dispensed at Visit 1 (Screening/Baseline; Day 1). As described in [Section 7.2.1](#), the subject will empty any remaining contents from the unit-dose dropper bottle following each instillation. The subject should then empty the remaining contents and return the opened bottle to its foil pouch and place it in the medication box for return to the study site. All opened bottles as well as any unopened study medication will be returned at Visit 2 (Treatment; Day 8) and Visit 3 (Treatment; Day 15).

At Visit 2, the box will be re-dispensed to the subject following study drug accountability and removal of opened study medication materials. Study medication accountability shall again be conducted at Visit 3, but the box will not be re-dispensed. The Investigator or designee must account for all received and returned study medication. The monitor will review dispensing and study medication accountability records during site visits and at the completion of the study and note any discrepancies.

4.4.4.2 Return of Study Medication

When the study is completed or is terminated by Ocuphire, all study materials, including used and unused study medication bottles, must be returned to Ocuphire (or its designee) or destroyed under the direction of same. All study medication accounting procedures must be completed before the study is considered completed. A final study medication disposition will be completed by the study coordinator.

4.5 Expected Duration of Subject Participation

The total length of subject participation is approximately 3 weeks, with 3 clinic visits and one telephone call follow-up summarized below:

- Visit 1 (Screening/Baseline)/Day 1
- Visit 2 (Treatment)/Day 8 (± 1 day)
- Visit 3 (Treatment)/Day 15 (± 1 day)
- Follow-up telephone call 1 to 3 days after Visit 3

The execution of the entire study (first subject screened through last randomized subject completed) is expected to be approximately 9 to 12 months.

4.6 Randomization and Procedure for Breaking the Code

A randomization code for allocating subjects to treatment will be prepared by a masked biostatistician not connected with the study. Subjects will be stratified by iris color (light/dark irides).

At the initiation of study-related procedures, every subject who is screened is assigned a ***subject identification number*** in numerical order within site. Once a subject is qualified for the study, the subject is assigned a ***randomization number*** in the order provided by the biostatistician.

The study medications will be masked to Investigators, study staff, study subjects, the clinical research organization (CRO), and Ocuphire. Only in case of medical emergency or occurrence of SAEs will the randomization code be unmasked by the Medical Monitor and made available to the Investigator, Ocuphire, and/or other personnel involved in the monitoring or conduct of this study.

4.7 Collection of Data

Study-specific data that have been outlined in the protocol will be entered into the clinical database by individual(s) designated by the Investigator. Data are verified electronically using a series of online programmed edit checks that have been created by the Clinical Data Manager and programmed by the Clinical Data Programmer or designee. Data discrepancies will be brought to the attention of the clinical team and investigated by the study monitor and site staff. Study monitors will review and verify a targeted subset of data collected in the electronic Case Report Form (eCRF) against any applicable source documentation during remote review or scheduled monitoring visits. The specific data selected for source data verification will be detailed in Clinical Monitoring Plan. The study monitor will work closely with the site staff to address any discrepancies that have been found so that proper resolutions can be made and documented in the clinical database. An audit trail within the system will track all changes made to the data.

4.8 Completed Subject

A completed subject is defined as one who completes all planned procedures through the end of Visit 3.

4.9 Non-completing Subject

A non-completing subject is defined as one who exits the study by their own volition or at the discretion of the Investigator and/or the Medical Monitor prior to completing all of the study procedures required in this protocol. Any subject may decide to voluntarily withdraw from the study at any time without prejudice.

4.9.1 Study Medication Discontinuation

The study medication may be discontinued for the following reasons:

- **Adverse Events:** AEs include clinically significant laboratory abnormalities and intercurrent diseases reported by the subject or observed by the Investigator with documentation on the eCRF.
- **Death:** If a subject dies, the AE that caused the death should be documented on the eCRF and be noted as serious and fatal.
- **Disallowed concurrent medication:** Any medication not allowed by the protocol would be a protocol violation.
- **Lack of efficacy:** A subject may elect to discontinue participation in the study for a perceived lack of efficacy.
- **Investigator decision:** A subject may be discontinued for reasons other than those bulleted previously if the Investigator thinks it is not in the best interest of the subject to continue.
- **Other:** If there is any other reason for subject discontinuation this should be noted on the eCRF.

The reason for premature study medication discontinuation should be entered onto the appropriate eCRF.

4.9.2 Reasons for Withdrawal From Study

- Subject withdraws consent.
- Subject is lost to follow-up.
- Subject withdraws for other reason.

4.9.3 *Entire Study Terminated*

The entire study may be terminated by Investigators or Ocuphire. Prompt, written notice of reasonable cause to the other party (Ocuphire or Investigators, respectively) is required. Prompt notice to the Institutional Review Board (IRB) and to regulatory authorities is also required.

4.9.4 *Actions After Discontinuation*

All subjects who discontinue study medication due to a report of an AE **must** be followed-up and provided appropriate medical care until their signs and symptoms have remitted or stabilized or until medical assessments have returned to acceptable or pre-study limits.

For any subject who chooses to withdraw consent or who is non-compliant, every possible effort should be made by the Investigator to assure the Day 8 Visit 2 mL CVA and other measurements are assessed prior to discontinuation, in addition to a follow-up telephone call that includes assessments for AEs, concomitant medications, and subject-evaluated conjunctival hyperemia.

4.10 *Completed Study*

The study is completed when all randomized subjects have completed the study, all eCRFs have been completed, and all eCRF data entered into the database. Final database lock will occur after the last randomized subject completes last visit, all data have been entered, and all queries have been resolved.

4.11 *Procedure After the Completion of the Study*

When the study is completed, the CRO will provide Ocuphire and the Investigator with a brief (i.e., 1-3 pages) report, containing a description of the study, the number of subjects enrolled, the number of subjects completed, the number of subjects who dropped out and why, efficacy findings, and AEs.

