- Subject shall be assessed for mLcVA, mHCVA, pLCVA, and DCNVA (mesopic, high-contrast conditions) as mentioned in [Section 4.1](#).
- OPD Scan measurements (for those sites with OPD Scan III), wavefront aberrometry (total and higher-order RMS) and corneal topography measurements under mesopic conditions, and other data captured
- Eye redness (conjunctival hyperemia) shall be assessed visually with a grading scale (0-3) using images from the CCLRU.
- Subject shall be assessed using biomicroscopy.
- Subject must have an IOP assessment.
- Subject shall be assessed using ophthalmoscopy.

7.2.4 *Follow-Up Phone Call Visit 4*

Up to 3 days after Visit 3, subjects will be called and asked if they had any problems with their eyes from the last visit, including whether their eyes are red, and if there have been any changes in their medical condition or concomitant medications since their last visit.

Any changes in the condition of the subject are recorded as an AE.

If an AE/adverse reaction is unresolved at the time of the last visit or if a subject reports a worsening of symptoms, every effort should be made to follow up until the AE/adverse reaction is resolved or stabilized, the subject is lost to follow-up, or there is other resolution to the event.

7.2.5 *Unscheduled Visits*

An Unscheduled Visit may be any visit to the Investigator other than the specific visits requested in the protocol as possibly required for the subject's ophthalmic condition. The Investigator will perform all procedures necessary to evaluate the study participant at these visits and record any AEs in the eCRF.

As noted in [Section 4.9.4](#), every possible effort should be made by Investigators to assure that subjects who discontinue early from the study have a telephone follow-up that includes assessments of AEs, concomitant medications, and subject-evaluated conjunctival hyperemia.

7.2.6 *Visit Variation*

Visit 2 on Day 8 and Visit 3 on Day 15 may each be 1 day late. If the visit is late, the subject should be advised to take an additional dose from 1 of the 2 spare dropper bottles provided in the study medication box the night before the visit. The subject should then empty the remaining contents and return the opened bottle to its foil pouch and place it in the medication box for return to the study site at their next visit. The follow-up telephone call may occur up to 3 days after Visit 3.

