7.1.1. Modified Intention-to-Treat (mITT)

The mITT will include all randomized subjects who received at least 1 dose of study medication and have a Baseline and any Day 8 efficacy measurement. The mITT will be used for the primary endpoint analysis and to analyze efficacy endpoints, with subjects included in their randomized treatment regardless of the treatment they actually received.

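### Protocol 4.9.4 seeks the Day 8 mLCVA only from consent withdrawers and non-compliers, so subjects stopped for an AE or by the Investigator can go unmeasured and fall outside the SAP's mITT

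*Protocol*

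**What the plan says.** The primary endpoint (Protocol 4.1) is the percentage of subjects gaining at least 15 ETDRS "letters (≥ 3 lines) of improvement in the study eye compared to baseline in monocular mLCVA at Day 8". One visit, Visit 2, supplies it.

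Protocol 4.9.1 begins "The study medication may be discontinued for the following reasons" and lists AEs, death, disallowed concurrent medication, lack of efficacy, Investigator decision and other. Lack of efficacy is worded as the subject's choice to leave: "A subject may elect to discontinue participation in the study for a perceived lack of efficacy". Protocol 4.9.2 lists withdrawal from the study separately.

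Protocol 4.9.4 then gives two instructions.
- Subjects who stop medication because of an AE must be "followed-up and provided appropriate medical care until their signs and symptoms have remitted or stabilized". No visual acuity measurement is mentioned.
- The second begins "For any subject who chooses to withdraw consent or who is non-compliant, every possible effort should be made by the Investigator". Its aim is that the Day 8 "Visit 2 mL CVA and other measurements are assessed prior to discontinuation, in addition to a follow-up telephone call".

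Protocol 7.2.5 covers early discontinuers in general and asks that "subjects who discontinue early from the study have a telephone follow-up that includes assessments of AEs, concomitant medications, and subject-evaluated conjunctival hyperemia". It does not mention mLCVA.

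SAP 7.1.1 limits the mITT to randomized subjects who "received at least 1 dose of study medication and have a Baseline and any Day 8 efficacy measurement". The mITT in Protocol 9.2 needs only one dose. SAP 9 declares the primary endpoint met or not on the mITT, with imputation, and makes the ARP analysis with imputation confirmatory. SAP 7.3.3 assigns early-termination data, including efficacy, to the closest visit.

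**The concern.** The protocol recognizes that the Day 8 mLCVA is worth an extra effort, but directs that effort only at consent withdrawers and non-compliers. Subjects taken off drug for an AE, or by the Investigator, are the ones whose stopping is most plausibly connected with treatment, and nothing readable directs the site to measure them.

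The SAP can then turn a missing measurement into an exclusion. A subject with no Day 8 efficacy data is not in the mITT, so imputation within the mITT cannot reach that subject. If such losses were more frequent in one arm and related to response, the deciding analysis would compare groups that are no longer fully protected by randomization.

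**Working it through.** **1. Planned loss.** Inputs: 136 evaluable subjects, 15% drop-out, 1:1 allocation (Protocol 9.1, SAP 6).
- 136 / (1 − 0.15) = 160, which reproduces the planned number randomized.
- Planned loss: 160 − 136 = 24, or 12 per arm if equal.
- This is all-cause drop-out, which the SAP places between Day 1 and Day 15. Losses before Day 8 for the reasons at issue are some unknown part of it.

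The response rates and power behind the 136 are redacted, so that figure cannot be re-derived.

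**2. Who is asked for the Day 8 mLCVA.**

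| Reason | Day 8 mLCVA effort (4.9.4) | Other instruction |
|---|---|---|
| Consent withdrawn, or non-compliant | Yes, before exit | Telephone call |
| AE | Not named | Medical follow-up; telephone call if leaving the study early |
| Investigator decision, or other | Not named | Telephone call if leaving the study early |
| Disallowed medication | Not named; a site might class it as non-compliance | Telephone call if leaving the study early |
| Lack of efficacy | Not named, but worded as the subject's election, so may be handled as consent withdrawal | Telephone call if leaving the study early |

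**3. What the SAP does next.** Take a dosed subject who stops for an AE on Day 3.
- Attends Visit 2 and has any efficacy measurement there, for example pupil diameter: stays in the mITT, and a missing mLCVA is imputed.
- Has efficacy measured at early termination: SAP 7.3.3 can assign it to Day 8, but the protocol does not ask for that measurement in this subject.
- Has no efficacy measurement after baseline: outside the mITT, and kept only in the ARP. The readable part of SAP 7.3.2.3 says imputation is done by arm from mLCVA at baseline and Day 8, so the imputed value would rest on subjects who were measured.

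**4. Possible size (illustration only).** Let the Nyxol arm have N = 80 with R = 13 responders. The 13 is an assumption. Let k subjects be lost, of whom r would have responded. The observed rate is (R − r) / (N − k). With nobody lost it is 13/80 = 16.3%.

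| Assumption about those lost | k = 6 | k = 12 |
|---|---|---|
| None would respond | 13/74 = 17.6% | 13/68 = 19.1% |
| Respond at about the arm's rate (r = 1; r = 2) | 12/74 = 16.2% | 11/68 = 16.2% |
| One third would respond (r = 2; r = 4) | 11/74 = 14.9% | 9/68 = 13.2% |

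The treatment difference moves by the Nyxol shift minus any placebo shift, so similar losses in both arms partly cancel. The k = 12 column takes the arm's whole planned drop-out as stops before Day 8, for reasons 4.9.4 does not cover, with no efficacy measured. It is an upper case.

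**The case against.** A reader might infer that anyone stopped for an AE or lack of efficacy leaves the primary analysis, and that this inflates the Nyxol responder rate by 1 to 3 points. The documents do not support that.

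- **Stopping drug is not leaving the study.** Protocol 4.9.1 and 4.9.2 separate the two, and SAP 8.1 tabulates them separately. A subject off drug but still enrolled may attend Visit 2, where mLCVA is a listed assessment (Protocol 7.2.2). This stands as a limit on the number lost. However, no readable section says that off-drug subjects attend, and the procedure rows of the visit schedules are largely redacted or missing.
- **Lack of efficacy may already be covered,** because it is worded as the subject's own election. This stands.
- **The mITT rule is lenient.** Any Day 8 efficacy measurement keeps a subject in. This stands; only subjects with none are excluded.
- **Mitigations exist.** SAP 7.3.3 and the ARP analysis both help, but only in part: the first needs a measurement nobody is told to take, and the second does not decide the endpoint.
- **Unequal AE stopping is not shown.** Hyperemia was the most frequent AE in earlier Nyxol studies (Protocol 8.3.1). But AEs were mild to moderate, bedtime dosing is said to lessen them, and the 14-day trial with the same evening schedule found no statistical difference in hyperemia from placebo (Protocol 2.2). No AE discontinuation rate is given for either arm. This stands: unequal loss is a risk, not a finding.
- **The upward direction is assumed.** It follows only if stoppers are non-responders, and the working shows no shift or a downward shift under other assumptions. This stands.

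**Conclusion.** The gap in data collection is real. Protocol 4.9.4 seeks the primary outcome from two groups of discontinuers and leaves out those stopped for an AE, Investigator decision, disallowed medication or other reasons. Those with no Day 8 efficacy data fall outside the population that decides the primary endpoint.

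Whether this biases the result cannot be told from the documents. Bias needs loss that differs by arm and relates to response, and neither is documented. The rise from 16.3% to 17.6% or 19.1% rests on the assumed 13 responders of 80, on every lost subject being a non-responder and, at the top, on all 12 planned drop-outs in the arm being unmeasured stops before Day 8. The shift is essentially nil if stoppers respond at the arm's rate. This is a cheap improvement worth making, not evidence that the primary analysis is biased.

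**What to change.** Keep the present sentence in Protocol 4.9.4 for consent withdrawers and non-compliers, including measurement before they leave. Replacing it with a single rule that exempts consent withdrawers would lose exit measurements now sought. Then add:

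> *For any other subject who discontinues study medication or the study before Visit 2, whatever the reason, the site should make the same effort to perform the Visit 2 (Day 8) mLCVA and other efficacy measurements in the scheduled window or, if the subject will not return, at the time of exit.*

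Align Protocol 7.2.5 so that it refers to these measurements as well as the telephone call. SAP 7.3.3 can already take in measurements made at exit, and analysis by randomized arm is already planned, so neither needs new text for this.

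The cost is one sentence, a cross-reference and a few off-treatment visits. The effect estimate may be somewhat diluted because some Day 8 values will come from subjects no longer on drug. The change concerns data collection only; no stopping rule or planned sample size changes. The difference between the protocol and SAP definitions of the mITT is a separate matter that this sentence does not resolve.
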